3.6 Allocation concealment

In this study, allocation concealment will be done at cluster level. A senior dental officer (SDO) in Kota Belud Dental District Office who is not involved in cluster identification and recruitment will keep the allocation sequence in a brown envelope in his or her SDO's office until the matched pair are ready to be recruited into the study.

The allocation sequence will be generated by a statistician employed at the Faculty of Dentistry, Universiti Malaya using computer generated tables. The information will be kept confidential until the intervention are assigned to the villages.

Within the cluster, a universal sampling technique will be used to recruit participants into the study. Universal sampling is also known as a total population sampling; which is a type of purposive sampling that involves examining the entire population that have a particular set of characteristics (Laerd Statistics, 2012). All eligible participants who fulfilled the inclusion and exclusion criteria through the screening session will be recruited as study sample. Thereafter, informed consent will be obtained from the participants.

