3.10.3.2 Implementation of the Study

Control Group

The community screening program for the control group will be organised at the community hall. Villagers who attended the screening program will first be registered and screened for eligibility to participate in the study (**Checkpoint 1**). The eligible participants will be briefed on the nature of the intervention and will be invited to participate. A copy of 'Patient Information Sheet' (PIS) (Appendix A) will be explained and given for reference about the study details and written informed consents (Appendix B) will be obtained from the villagers prior admitting them into the study.

Only consented participants will be interviewed by the trained interviewers (**Checkpoint 2**). Information regarding demographics details and baseline information of BQ chewing behaviours, BQ composition, BQ dependency levels, reasons for chewing, readiness and self-perceived barriers to quit will be obtained. No intra-oral clinical examination will be carried out in this study.

Upon completing of the interview, participants will be given an educational booklet which contains general information regarding AN and BQ, risk associated with BQ chewing behaviour, cessation strategies that are modeled after tobacco cessation and researcher's contact information. After an one-to one explanation about the educational booklet to the participants by the interviewer, they will be ushered to saliva collection counter (**Checkpoint 3**) to provide their baseline saliva sample. Participants will be thanked and given a token of appreciation before they are ushered out of the community hall.

Participants will be provided with an appointment card to return on the 22-day, 1-month and 3-month for follow-up. Follow-up questionnaire and saliva samples will be taken on 22-day and 3-month, whereas a community perception analysis will be performed at 1-

month together with completion of follow-up questionnaire. The summary of participant's flow for the control group is illustrated in Figure 3.6.

[figure not shown]

Figure 3.6 Summary of Participant's Flow for the Control Group in this study

Intervention group

Screening (Day 0)

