The community screening program for the intervention group will be organised at the community hall on a Saturday. Villagers who attend the screening program will first be registered and screened for eligibility to participate in the study (**Checkpoint 1**). The eligible participants will be briefed on the nature of the intervention and will be invited to participate. A copy of 'Patient Information Sheet' (PIS) (Appendix A) will be given for the reference about the study details and written informed consents (Appendix B) will be obtained from the villagers prior admitting them into the study.

Only consented participants will be interviewed by the trained interviewers (**Checkpoint 2**). Face-to-face interviews will be carried out to gain participant's information regarding demographics details and baseline information of BQ chewing behaviours, BQ composition, BQ dependency levels, reasons for chewing, readiness and self-perceived barriers to quit habit. No intra-oral clinical examination will be carried out in this study.

Upon completion of the interview, participants will be briefly explained and given an educational booklet which contains general information regarding AN and BQ, risk associated with BQ chewing behaviour, cessation strategies that are modeled after tobacco cessation and researcher's contact information. They will then be ushered to saliva collection counter (**Checkpoint 3**) to provide their baseline saliva sample.

Participants will be thanked and given a token of appreciation before being ushered out of the community hall and will be reminded to return the next day (Sunday) to initiate the first support session for the cessation intervention. For every intervention session attended by the participants, they will be monetarily incentivized for their time and commitment for cessation. Appointment card will be provided to ease participants reference of support session dates.

A self explanatory video presentation regarding general information of AN and BQ, the ill health effects of BQ and introduction and importance of cessation program will be continuously played **for the non- chewers in the village hall** to increase their knowledge and awareness while they are waiting for their family members. who are undergoing the screening. This can help maximise their support for their loved ones who are trying to quit the risk habit.

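### The allocation envelope may be opened before villagers are screened and consented, so village-level concealment does not protect individual recruitment

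*Protocol*

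**What the plan says.** Section 3.6 places concealment at cluster level. A senior dental officer who takes no part in identifying or recruiting clusters keeps the sequence "until the matched pair are ready to be recruited into the study", and a second sentence adds that "The information will be kept confidential until the intervention are assigned to the villages". On individuals, the same section states: "All eligible participants who fulfilled the inclusion and exclusion criteria through the screening session will be recruited as study sample". Consent follows: "Thereafter, informed consent will be obtained from the participants".

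Section 3.10.3.2 describes Day 0 twice, once per arm. For control, "The community screening program for the control group will be organised at the community hall"; for intervention, "The community screening program for the intervention group will be organised at the community hall on a Saturday". In both, the order is registration and eligibility check, briefing and invitation, information sheet and consent, interview, booklet, saliva. The two days differ in these ways:

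- **Booklet.** In control it is handed over with an individual explanation ("After an one-to one explanation about the educational booklet to the participants by the interviewer"); in intervention the explanation is brief.
- **Appointments.** In control, "Participants will be provided with an appointment card to return on the 22-day, 1-month and 3-month for follow-up". In intervention the card lists support-session dates, and participants are reminded to come back the next day for Session 1.
- **Other.** Intervention participants are paid for each session attended, and a video that introduces the cessation programme plays in the hall for non-chewers. The control description mentions neither.

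Section 3.7 says that only the implementing researcher knows who receives the intervention. Section 3.8 excludes people not willing to quit and those judged unable to comply.

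**The concern.** Randomising villages balances the people who could be recruited. It does not balance those who attend, are judged eligible and consent, if any of these steps is taken with the arm known. Here, eligibility rests partly on judgement (willingness to quit, ability to comply) and attendance is promoted through the village head.

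At stake is the 3-month cessation comparison in section 1.7. Selection could run either way. Keener quitters might come forward, or be encouraged, where the full programme is offered; payment per session might instead draw less committed chewers. Adding villages would not remove a systematic difference of this kind. The baseline readiness and dependency items would show only the part of it that they measure.

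**Working it through.** **Step 1: order of events, from the text.**

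| Event | Where | Timing |
|---|---|---|
| Promotion through the village head | 3.10.3.1 | 3 weeks before implementation; not split by arm |
| Envelope may be opened | 3.6 | When the pair is ready for recruitment |
| Screening, briefing, consent, interview, booklet, saliva | 3.10.3.2 | Day 0, described separately by arm |
| Session 1 (intervention only) | 3.10.3.2 | Day 1, the day after screening |

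Section 3.6 uses the word recruited for what happens to individuals through the screening session, so readiness for recruitment comes before screening. If the word refers instead to enrolling the villages as clusters, the envelope opens no later. No single sentence states the order, so this is an inference. The field schedule supports it: session dates are issued on Day 0 and Session 1 is the next day, so the arm has to be known by Day 0. No visible text places consent or baseline before the envelope is opened, or gives recruitment to staff unaware of the arm.

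**Step 2: who knows what.** Section 3.7 gives the arm to the implementing researcher, so that person knows it when residents are screened. For residents, the promotion and the pre-consent briefing are worded alike in both arms, and each person's booklet and card come after consent. Two routes remain possible: people still queuing while others finish, and the village head, who is told that his villagers will receive the intervention. What a control village's head is told is not stated.

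**Step 3: illustration of size (assumed, not estimated).** The planning rates in section 3.4 are 9.09% (control) and 38.64% (intervention), a difference of 38.64 - 9.09 = 29.55 points. The stated 38 per arm reproduces with the two-sided, continuity-corrected two-proportion formula at alpha 0.05 and power 0.8 (32 per arm without the correction).

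Suppose a factor that doubles the quit chance is held by a share q0 of control and q1 of intervention entrants. The doubling is borrowed from section 2.4.2, which reports ex-smokers as twice as likely to quit as current smokers; the shares are assumed. With no programme effect and the control rate fixed at 9.09%:

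intervention rate = 9.09% x (1 + q1) / (1 + q0)

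| q0, q1 | Rate | Shift (points) | Shift / 29.55 |
|---|---|---|---|
| 0.25, 0.45 | 10.54% | +1.45 | +4.9% |
| 0.25, 0.75 | 12.73% | +3.64 | +12.3% |
| 0, 1 | 18.18% | +9.09 | +30.8% |
| 0.45, 0.25 | 7.84% | -1.25 | -4.2% |
| 0.75, 0.25 | 6.49% | -2.60 | -8.8% |
| 1, 0 | 4.55% | -4.55 | -15.4% |

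Exact binomial enumeration with 38 per arm, two-sided 5% level, individuals treated as independent (clustering ignored), gives these false-positive rates:

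| Shift (points) | Fisher | Uncorrected chi-square |
|---|---|---|
| 0 | 1.3% | 5.8% |
| +1.45 | 1.7% | 6.4% |
| +3.64 | 3.2% | 8.8% |
| +9.09 | 12.8% | 21.9% |

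One extra entrant in an arm who would have quit anyway moves that arm by 1/38 = 2.6 points.

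**The case against.** The strongest reply is that the text does not show residents knowing their arm before consent. The promotion is common to both arms, the briefing-and-invitation sentence is the same in both, every entrant must agree to five sessions, and for each person the arm-specific steps come after consent. Section 3.7 says that only the implementing researcher knows the arm. People in the queue have already attended, so leakage there cannot affect attendance. The information sheet, the consent form and several flow figures are not in the text available here and may say more. All of this stands, so a reader who infers that residents are told their arm before consenting goes beyond the document.

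It does not dispose of the point. Staff knowledge is enough to influence a judgement on willingness to quit or ability to comply, and how warmly a person is invited. Blinding residents does not blind the recruiter. Recruiting all eligible attenders limits staff choice but leaves those judgements open.

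The illustration is also fairly criticised. The shares are invented and the doubling comes from Taiwan. Section 2.1 reports that most Malaysian female chewers chew without smoking (27.8%, against 1.2% who also smoke). The mildest imbalance barely moves the false-positive rate, and the largest figures need complete separation on the factor.

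**Conclusion.** The point holds as a weakness in procedure: the implementing researcher knows a village's arm by the time its residents are screened and consented, and residents may learn it. Concealing the village sequence therefore does not protect individual recruitment.

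Size and direction are unknown. Under the assumptions shown, moderate imbalances give shifts of about 1 to 4 points, and the full range is -4.5 to +9.1 points. A reader might infer that selection could account for the planned effect. The figures do not support this: even complete separation on a twofold factor gives under a third of 29.55 points. Nor do they show that selection will occur. The case for change rests on an avoidable exposure that is cheap to close. The order of unsealing and consent is a field procedure, and later analysis can adjust only for what was measured. The change should be made; confidence is medium, because the order of events is inferred and some pages are not visible.

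**What to change.** In sections 3.6 and 3.10.3:

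1. Use the same promotion and the same briefing in both villages of a matched pair, including what the village head is told.
2. Complete screening, consent, baseline interview and baseline saliva in both villages, with identical Day 0 steps and the same booklet explanation.
3. Only then have the senior dental officer open that pair's envelope and record the date.
4. Issue session appointments and show programme-specific material, including the video, after that.

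This uses the officer, envelope and matched pairs already planned and adds no planned participants. Because the main researcher collects and transports the saliva, the two villages of a pair will probably need separate screening days. Session 1 would then start some days after baseline, about a week if sessions stay at weekends, and the July to September timetable needs a small adjustment. A few consented people may be lost in the gap, within the planned margin of 46 - 38 = 8 per arm. That loss would occur with the arm known, so some selection could reappear there, but those people are counted and have baseline data, unlike people who never attend.

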3.7 Blinding

This study will utilise a single-blinding strategy in which only the researcher implementing the study knows which participant is receiving intervention until the trial is over. A single-blind study makes results of the study less likely to be biased. This means that the results are less likely to be affected by factors that are not related to the intervention being tested.

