3.0 MATERIALS AND METHOD

3.1 Overview of the Study design

This is a comparative prospective community trial which utilises a cluster randomised controlled trial design involving a Bajau indigenous community in Sabah, Malaysia with a 1:1 allocation ratio. The clusters are Bajau villages that practises BQ chewing habits in Kota Belud district in Sabah. The Bajau villages are the unit of randomisation. There are 39 Bajau villages in Kota Belud, Sabah (Tahir Z et al., 2003).

The clustered randomised controlled trial study design was selected as there was a high tendency of crossover if both intervention and control groups are randomised within the same village. Individuals allocated to a control group may inadvertently receive some aspects of the intervention if they are in proximity to the individuals in intervention group (Hahn S et al (2005). Thus, clustered randomised trial is the best available design for researchers who evaluating intervention that operates at group level, that manipulates the social and physical environment and cannot be delivered to individual participants without any substantial risk of contamination (NIH, 2022).

The eligible villages will be randomised into intervention and control groups based on the required sample size. The intervention group will receive an educational booklet and a structured BQ cessation program which will be cross- culturally adapted first based on a clinical trial (BENIT) by Paulino YC et al. (2020) for a Malaysian high risk population. The control group will only receive an educational booklet.

Baseline information on participant's demographics, BQ chewing behaviours, BQ composition, BQ dependency levels, reasons for chewing, the readiness and self perceived barriers to cease habit will be obtained prior to the commencement of the intervention. The

same participants will be followed-up at 22-day and 3-month after commencement of intervention to assess their of quitting experience and impact of the intervention. Day 22 follow-up was kept in this study as it will enable study results to be compared with similar BQ cessation studies in other parts of the world such as in Pacific Islands (Moss J. et al., 2015 and Paulino YC et al., 2020).

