3.8 Selection criteria

The **inclusion criteria** for this study is as follows:

- ✚ A self-reported BQ chewer who has been chewing BQ for the past 6 months with atleast 2-3 chewing episode per week. The ingredient of BQ must include AN without or without smokeless tobacco.
- ✚ Other optional ingredients such as slaked lime and betel leaf are allowed.
- ✚ Age of participant must be 18 year old or above
- ✚ Participants must be residing in study location (Kota Belud, Sabah)
- ✚ Ability to comprehend, converse and read in Bahasa Melayu and their local language (Bajau)
- ✚ Participants who are able to provide written consent and agree to comply with all protocol-specified procedures such as providing saliva samples, participating in five 1-2 hours sessions of intervention over 22 days and agree to attend follow-up sessions on first and third month

The **exclusion criteria** for this study are as below:

- ✚ Non-Malaysian citizen
- ✚ Participants who are not willing to quit the BQ chewing habit at the time of the study
- ✚ Women who are pregnant or nursing at the time of study
- ✚ Individuals with psychiatric illness or special social situations that would limit their compliance with study requirements

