3.10.2.3 Training of Intervention Facilitators

A two days training will be conducted by the main researcher. Seven to eight staff who are identified by the Senior District Officer will be involved as questionnaire and worksheet interviewers and verbal translators for this study. Dental officers, dental therapists and dental assistants will be the staff of choice to be the facilitators in this study. They are required to be conversant in Bajau language; especially to support the older section of the participants who are more familiar in their local dialect.

The task of the staff is to explain the questionnaire and worksheets items and to be able to assist participants to complete them as accurately as possible. During the talk sessions, the staffs will act as verbal translators and also assist in the question and answer sessions. The delivery of cessation intervention will mainly be in Malay language delivered by the main researcher. The staff will also assist to collect and verify the responses given by participants in the homework logs such as trigger monitoring logs, trigger management, the non chewing game plan worksheets, social support and thought management worksheets.

During the training, the staff will be introduced to the intervention program; the aims and objectives to achieve, the number and brief explanation about the support sessions and the other method of evaluation at the end of the program. A simulation session will be planned to practically expose the staff to the order and details of this intervention. Staff who are not involved in this study will be recruited to act as a BQ chewers to train the staff who are selected to be the facilitators. The names of all the facilitators will be presented and registered under the National Medical Research Registry (NMRR), Ministry of Health (MOH), Malaysia.

Through the simulation, the main researcher could gain some insight on the possible shortcomings or issues that may arise during implementation. Appropriate remedial action and modification can done before intervention commences. A training manual will be prepared for each staff.

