The subjects will be assigned into a group of seven participants and the appointments for each group participants will be given across the week. A total of 2 group sessions will be made in a day; a morning session and an afternoon session. Participants will be sought of their preferred time to increase participation in the intervention group.

[figure not shown]

Figure 3.7 Flow of Participants on the Screening of the study (Day 0)

1st Session (Day 1)

On the **1st session of the intervention (Day 1)**, attendance of all eligible and consented participants will be taken at **Checkpoint 1** and the nature of intervention will be introduced through a **brief talk**. The information that the participants will undergo 5 sessions of support and information group designed to assist them to quit BQ chewing habit over 22 days period will be emphasized and they will be reminded that their continuous commitment to the intervention is utmost important to their future cessation.

They will also be briefed that each support session will consume approximately 1-2 hours. It will be conducted by the main researcher in Malay language (Bahasa Melayu) and

translated by trained facilitators into Bajau language verbally. A translation script will be prepared before initiation of the intervention for standardization to minimise bias or any poor explanation in Bajau language.

After the brief introduction, an **educational talk** will be delivered to the study participants by the main researcher. The content of the talk will be based on the topics of the educational booklets (general information regarding AN and BQ, risk associated with BQ chewing behaviour through projection of captivating graphical aids, cessation strategies that are modeled after tobacco cessation and researcher's contact information) but in a more detailed and interactive manner. An aid of Microsoft Powerpoint multimedia presentation will be used. A two-way communication mode will try to be sought throughout the entire talk. Participants will be encouraged to participate actively during the educational talk session. The aim of the educational talk is to increase the chewer's awareness, motivation and to enhance their commitment to cease behaviour. Participants too will be encouraged to share their experience and their feelings of chewing BQ and what are the challenges they face while practicing this habit.

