3.11 Saliva Test Protocol

3.11.1 Saliva Collection

The saliva collection tool should be about 20 mL in length and in a conical shape polypropylene tubes. An amount of 1 – 2 mL saliva sample will be collected during assessment by the Main Researcher via ‘passive drool’ method and initially stored at –20°C after collection in an insulated cooler box with reusable ice packs. The Main Researcher will transport the biospecimen to the Biotechnology Research Institute (BRI), Universiti Malaysia Sabah (UMS). Upon arrival to the lab, it should be stored at –80 °C until analysis is done (Paulino YC et al., 2020).

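### Section 3.7 claims single-blinding and lower bias, but participants and facilitators know the arm, so the self-reported primary outcome is open to differential over-reporting that saliva testing only partly offsets

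*Protocol*

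**What the plan says.** Protocol 3.7 describes a single-blind strategy in which "only the researcher implementing the study knows which participant is receiving intervention until the trial is over", and draws the benefit from it: "A single-blind study makes results of the study less likely to be biased".

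Other sections describe what participants and staff see:

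- **Arms (3.1).** The intervention villages receive the structured programme and a booklet. For the others, "The control group will only receive an educational booklet".
- **Eligibility (3.8).** One list serves both arms. It requires agreement to "participating in five 1-2 hours sessions of intervention over 22 days".
- **Screening day (3.10.3.2).** The control-group and intervention-group descriptions both state: "The eligible participants will be briefed on the nature of the intervention and will be invited to participate".
- **Session 1 (3.10.3.2).** Intervention participants are told that "the participants will undergo 5 sessions of support and information group designed to assist them to quit BQ chewing habit". They are paid for each session attended.
- **Staff (3.10.2.3).** Seven to eight clinic staff "will be involved as questionnaire and worksheet interviewers and verbal translators for this study". The same paragraph calls them the facilitators, and 3.14.1 again describes the facilitators being trained on the questionnaire and the worksheets. The main researcher delivers the sessions.
- **Saliva (3.11.1).** The "saliva sample will be collected during assessment by the Main Researcher". A separate university laboratory runs the assay (3.11.5).
- **Outcomes (3.12, 3.14.2, 3.14.3).** The primary outcomes are self-reported quitting at Day 22 and Month 3, obtained by face-to-face interview. Salivary biomarkers are secondary and are meant to verify the self-report.

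**The concern.** A behavioural cessation programme can hardly be hidden from those who attend it, and running it open-label is acceptable. The fault is that 3.7 claims a masking the trial does not have and then takes reassurance about bias from it.

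This matters because the primary outcome is an answer given in person. Intervention participants have been coached towards a quit day, and their Day 22 answer is taken on arrival at session 5, seven days after that quit day. They have a reason to report success that control participants have to a lesser degree. If over-reporting differs between arms, the primary comparison shows a difference in cessation that is partly or wholly a difference in reporting. A reader who relies on 3.7 would discount that risk.

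**Working it through.** **1. The blinding claim against the rest of the protocol**

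| Who | What 3.7 implies | What other sections show |
|---|---|---|
| Participants | Unaware | Briefed on the intervention (3.10.3.2), agree to five sessions to be eligible (3.8), then attend five sessions or receive a booklet |
| Facilitators | Unaware | Present at the sessions in intervention villages (3.10.2.3, 3.10.3.2) |
| Follow-up interviewers | Unaware | Not named in 3.14.2 or 3.14.3. The only interviewers described are the facilitators (3.10.2.3, 3.14.1), so overlap is inferred |
| Main researcher | Aware | Delivers the sessions and collects the saliva |
| Laboratory staff | Unaware | Masking not stated either way (3.11.5) |

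The claim fails for participants and facilitators on the text alone, whoever conducts the follow-up interviews.

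**2. The plan's own sample size**

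Inputs from 3.4: p1 = 0.3864, p2 = 0.0909, alpha 0.05, power 0.8, ratio 1:1. Sidedness is not stated; two-sided is tried.

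- Difference d = 0.2955; mean rate 0.23865.
- n0 = [1.960 × √(2 × 0.23865 × 0.76135) + 0.842 × √(0.3864 × 0.6136 + 0.0909 × 0.9091)]² / 0.2955² = 31.5, so 32 per arm uncorrected.
- With continuity correction, n = (n0/4) × [1 + √(1 + 4/(n0 × d))]² = 37.9, so 38 per arm and 76 in total.

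This matches the protocol, so the point does not rest on an arithmetic error.

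**3. What differential over-reporting would do**

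Set the true quit rate to 9.09% in both arms. A fraction f of intervention non-quitters and g of control non-quitters say they have quit. The reported rates are then 0.0909 + 0.9091f and 0.0909 + 0.9091g. The documents give no misreporting rate, so f and g are assumptions shown over a range. The probability of two-sided p < 0.05 comes from exact enumeration of both binomials at 38 per arm, ignoring village clustering.

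| g (control) | f (intervention) | Reported rates | Chi-square, uncorrected | Fisher exact |
|---|---|---|---|---|
| 0 | 0 | 9.1% vs 9.1% | 5.8% | 1.3% |
| 0 | 10% | 9.1% vs 18.2% | 21.9% | 12.8% |
| 0 | 20% | 9.1% vs 27.3% | 55.7% | 44.8% |
| 5% | 10% | 13.6% vs 18.2% | 8.6% | 4.7% |
| 5% | 15% | 13.6% vs 22.7% | 17.6% | 11.5% |
| 10% | 15% | 18.2% vs 22.7% | 7.8% | 4.6% |
| 10% | 20% | 18.2% vs 27.3% | 15.6% | 10.4% |

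At the dropout-inflated 46 per arm, the chi-square figures for f = 10% and 20% with g = 0 are 25.9% and 64.8%. Over-reporting by 0.2955 / 0.9091 = 32.5% of intervention non-quitters, with none in controls, would reproduce the whole assumed effect.

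**4. How far saliva protects**

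Saliva is taken at both primary time points with fixed cut-offs (3.12.2). Section 2.11 limits the areca markers to 8 hours or less after chewing, and visits are by appointment. A participant who chews but holds off before the visit can therefore test negative. The biomarkers are a secondary outcome, and 3.12.1 defines the primary one by self-report alone. The mitigation is real but partial.

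**The case against.** Several objections have force.

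- **A reader might infer that the primary answer is wholly unverified.** The documents do not support that: 3.14.2 and 3.14.3 collect saliva at both time points expressly to verify self-report, and the stated aim combines the two. What stands is that verification is secondary and its window short.
- **A reader might infer that nobody in the trial is masked.** That goes too far. The assay is run by laboratory staff at another institution, and the protocol does not say whether they know arm or village. Silence on tube labelling is not evidence of unmasking.
- **A reader might take it as stated that facilitators conduct the follow-up interviews.** Sections 3.14.2 and 3.14.3 name nobody. The inference is reasonable, and strongest for Day 22 in the intervention arm. It is weaker for Month 3 and for control villages, where no sessions are run.
- **The 22–56% assumes that controls never over-report.** Controls also receive a one-to-one explanation, a token and return appointments, and people unwilling to quit are excluded from both arms. With control over-reporting of 5–10% the figure falls to about 8–18%. A continuity-corrected chi-square gives 11–42% in the scenario with none in controls.
- **Changing the interviewer does not mask participants.** That is true. A colleague from the same clinic who attends session 5 also sees which arm it is. Reassignment removes only the pressure of answering one's own coach.

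None of this rescues 3.7. Intervention participants know that they attend sessions, and facilitators know that they run them.

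**Conclusion.** The point holds as a wrong statement in 3.7 with a plausible, directional consequence for the primary outcome. The mislabelling is certain from the text. The bias is a risk, not a finding: its size depends on assumed over-reporting, on a true rate of 9.09% in both arms, on 38 per arm and on ignoring clustering. Under those assumptions the chance of a falsely significant uncorrected chi-square ranges from about 8% to 56% (Fisher about 5% to 45%), depending on how far over-reporting in the intervention arm exceeds that in controls. These are not forecasts of the trial's error rate. Only the excess matters: equal over-reporting of 5% or 10% in both arms leaves the chi-square near its nominal level (5.5% and 5.1%). The correction should be made before recruitment, but the point is no argument against an open-label design.

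**What to change.** - **In 3.7**, replace the single-blind claim and the statement on bias. Describe the trial as open-label for participants, facilitators and the main researcher.
- **In 3.14.2 and 3.14.3**, name who conducts the Day 22 and Month 3 interviews. Assign them, from the seven to eight staff already trained, to people who did not facilitate in that village. Keep the main researcher out of these interviews.
- **In 3.11**, label tubes with study ID only, so that laboratory staff do not know arm or village.
- **Also in 3.7**, state what this does not achieve: it lessens the pressure to report success to one's own coach, but participants stay unmasked and interviewers are not fully masked, because village allocation is visible.

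The cost is rostering and labelling within the existing team. The downside is somewhat fewer facilitators at sessions in each intervention village, which needs checking against the number of checkpoints per session. Sample size and endpoint definitions do not change.
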